#### 2. OBJECTIVES

#### 2.1 Primary Objective

The primary objective is to determine the proportion of subjects who are insulin independent at  $75 \pm 5$  days following the first islet transplant among subjects treated with an experimental islet transplant immunosuppression regimen which includes rituximab and excludes tacrolimus.

This group will be compared, as a secondary analysis, to subjects in a concurrent protocol, CIT-07, which uses a standard immunosuppressive regimen.

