### 2.2 Secondary Objectives

The primary and secondary endpoints will be evaluated in this trial. Endpoints will be compared to corresponding endpoints in the CIT07 study.

In addition to achieving insulin independence, we hope to demonstrate that islet transplantation can result in near-normal glycemic control with amelioration from excessive glycemic lability and severe hypoglycemic episodes, and in an improved quality-of-life (QOL). Then the degree and durability of these responses will be determined.

Assessment for progression or development of secondary diabetes complications will include retinal photography, urinary albumin excretion (UAE), and GFR. Finally, we will monitor for procedural complications and AEs related to the immunosuppression regimen.

As previously mentioned, a drawback of the Edmonton approach is the use of CNI agents with known nephrotoxic and diabetogenic side effects. In fact, it's been recognized that some patients transplanted according to the "Edmonton protocol," who have early nephropathy, will experience a deterioration of renal function, mandating discontinuation of tacrolimus. Therefore, the large subset of T1D patients with early nephropathy are currently excluded from clinical islet transplantation trials due to the use of tacrolimus. In this regard, our pre-clinical results in NHP recipients (please see Preclinical Studies) have indicated that combined B- and T- lymphocyte immunotherapy (using a combination of rituximab and Thymoglobulin®), may obviate the need for tacrolimus maintenance therapy. Thus, we will determine the feasibility of a CNI free regimen in human islet transplantation by eliminating the tacrolimus used in the control arm (CIT-07) with the addition of rituximab during the initial induction of immunotherapy in the experimental arm (CIT-05). The benefit or harm of eliminating tacrolimus will be assessed by determining the proportion of subjects who remain insulin-independent at 365 days following the last islet transplant.

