The therapeutic trough level for sirolimus will be lowered to 10 - 12 ng/mL three months following the last islet infusion, or earlier if intolerable mouth ulcers or myelosuppression develops. If therapeutic trough levels of sirolimus cannot be maintained, mycophenolate mofetil (MMF, 500-1500 mg twice daily) may be added to ensure adequate immunosuppression: alternatively, sirolimus may be replaced by tacrolimus at a dose of 0.015 mg/kg PO BID adjusted to maintain trough levels of 6 - 10 ng/mL with the addition of mycophenolate mofetil (MMF, 500 - 1500 mg twice daily).

[figure not shown]

Figure 1: Study design diagram

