# 5.2.1.3 Sirolimus (Rapamune®)

Sirolimus will be administered at an initial dose of 0.2 mg/kg PO on day -2 relative to islet transplant, followed by 0.1 mg/kg QD. The daily dose will be adjusted to the whole blood 24-hr trough to target, as tolerated, 12-15 ng/mL for the first 3 months and 10-12 ng/mL thereafter. If a subject develops intolerable or clinically undesirable side-effects related to sirolimus therapy, his/her therapy may be converted to maintenance mycophenolate mofetil (MMF) at the discretion of the principal investigator.

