# 5.2.1.4 Tacrolimus (Prograf®)

Tacrolimus may be used as a replacement for sirolimus if sirolimus is not tolerated. Tacrolimus will be administered at an initial dose 0.015 mg/kg PO BID with the whole blood 12-hr trough adjusted to 6-10 ng/mL. Should subjects experience a decrease in their GFR of  $\geq$ 33% compared with baseline, a nephrology consult will be obtained, and tacrolimus target trough levels will be reduced by 25% should CNI toxicity be suspected as the primary cause for the decline in renal function.

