# 5.2.1.6 Mycophenolate Mofetil (CellCept®)

Mycophenolte mofetil may be used if sirolimus levels cannot be maintained  $\geq 10$  ng/mL. Mycophenolate mofetil will be administered at a dose of 500 to 1500 mg PO BID in addition to either tacrolimus or sirolimus. Subjects must practice two methods of contraception while taking MMF. If a subject experiences severe neutropenia (absolute neutrophil count  $<1x10^9/L$ ) while taking mycophenolate mofetil, mycophenolate mofetil exposure will be reviewed and

mycophenolate mofetil administration will be adjusted as part of the study protocol's neutropenia management plan.

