# 5.7.1.5 Nephrotoxicity:

A sustained 33% increase in serum creatinine or a 33% decrease in GFR warrants a prompt referral to a nephrologist for evaluation. If it is determined that the decrease in renal function is attributable to CNI immunosuppressive therapy, the treating physician should chose ONE of the therapeutic alternatives shown in the following table:

Table 2: Response to nephrotoxicity

Allowable therapeutic responses to CNI-induced nephrotoxocity	Rationale
Discontinue sirolimus, and replace it with mycophenelate mofetil or mycophenolate sodium.	The nephrotoxic effect of CNIs is increased by concomitant administration of sirolimus 123, 157.
If the trough sirolimus level is maintained at >10 ng/mL without adverse effects, discontinue the CNI and replace it with mycophenolate mofetil or mycophenolate sodium.	CNI should be discontinued only if the subject can tolerate a trough level of sirolimus that will result in adequate immunosuppression.
Decrease the target CNI trough level by 25%.	CNI toxicity is dose-related.

A repeat assessment of GFR should be performed 3 months after the change in immunosuppression.

Anti-hypertensives, anti-hyperlipidemics and other approved therapies for pre-existing and new medical conditions will be provided per standard of care.

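### The rules for subjects who cannot stay on sirolimus contradict each other, and a subject converted to a calcineurin inhibitor (CNI) counts as a success of a regimen defined as excluding tacrolimus, with no CNI-free result reported beside it

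*Protocol*

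**What the plan says.** Section numbers are those of the CIT-05 protocol. Section 3 makes sirolimus the only maintenance drug. The primary objective (Section 2.1) concerns an "immunosuppression regimen which includes rituximab and excludes tacrolimus". Section 2.2 adds: "The benefit or harm of eliminating tacrolimus will be assessed by determining the proportion of subjects who remain insulin-independent" at 365 days after the last transplant.

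Several places cover the subject who cannot stay on sirolimus:

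- Section 3: if therapeutic troughs cannot be held, MMF may be added; alternatively "sirolimus may be replaced by tacrolimus at a dose of 0.015 mg/kg PO BID", together with MMF.
- Section 5.2.1.3: for intolerable or undesirable side effects, "his/her therapy may be converted to maintenance mycophenolate mofetil (MMF) at the discretion of the principal investigator". No partner drug is named.
- Section 5.2.1.4: "Tacrolimus may be used as a replacement for sirolimus if sirolimus is not tolerated". If GFR falls by at least 33% and CNI toxicity is suspected as the main cause, the target trough is cut by 25%.
- Section 5.2.1.5: cyclosporine may take the place of tacrolimus.
- Section 5.2.1.6: MMF may be used if sirolimus cannot be held at 10 ng/mL or above, and is given "in addition to either tacrolimus or sirolimus".
- Section 5.2.1.7: mycophenolate sodium may replace tacrolimus, sirolimus or MMF.
- Section 5.6: tacrolimus is listed with rapamycin as a maintenance drug of this protocol.
- Section 5.7.1.5, Table 2: three alternative responses to CNI nephrotoxicity, the first being "Discontinue sirolimus, and replace it with mycophenelate mofetil or mycophenolate sodium".

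The insulin-independence definition in Section 3.1 has criteria on insulin use, HbA1c, glucose and c-peptide, and none on immunosuppression. Sections 7.1 and 10.1 put every transplanted subject in the analysis by intention to treat. Section 10.2.1 classes death and withdrawal of consent as failure, and imputes failure for other missing evaluations unless a later one exists. Conversion to a CNI is not mentioned. The incidence of regimen change is a safety endpoint only.

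**The concern.** There are two linked problems. First, two subjects in the same position could be treated differently, each in line with some section, because the sections do not fit together. What a converted subject received would then depend partly on the section followed.

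Second, the protocol fixes both the outcome rule and its interpretation, and they do not match. A subject moved to tacrolimus before Day 75 or Day 365 who is insulin independent at the visit enters the numerator of a rate that Sections 2.1 and 2.2 describe as belonging to a regimen without tacrolimus. With 12 subjects, one or two such cases matter to the reading of the result. The protocol does not cross conversion with the endpoint, so its specified results would not show how many successes were CNI-free.

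**Working it through.** **1. The passages side by side**

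- *Role of MMF.* Section 5.2.1.3 allows conversion from sirolimus to maintenance MMF. Section 5.2.1.6 gives MMF only alongside tacrolimus or sirolimus. A subject converted to MMF alone fits the first and not the second.
- *Trough trigger.* Section 3 acts when the therapeutic trough cannot be maintained: 12–15 ng/mL until three months after the last infusion (earlier if mouth ulcers or myelosuppression force a reduction), then 10–12. Section 5.2.1.6 acts below 10. In the first period, which includes Day 75, a trough from 10 to just under 12 meets one trigger and not the other. Afterwards both floors are 10.
- *CNI nephrotoxicity.* Section 5.2.1.4 sets one response, the 25% trough cut. Table 2 offers a choice of three, of which that cut is one. Rows 1 and 2 assume sirolimus and a CNI given together. No stated CIT-05 regimen does this: in Sections 3 and 5.2.1.4 tacrolimus replaces sirolimus, and the Appendix 1 footnote on tacrolimus levels says the same. Sirolimus with tacrolimus is the CIT-07 regimen (Section 1.1).
- *Maintenance drugs.* Section 5.6 names tacrolimus as one; Section 3 says sirolimus only.

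**2. How a converted subject is scored**

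The definition has no immunosuppression criterion (3.1), all transplanted subjects are included (7.1, 10.1), and conversion is not among the failures (10.2.1). It follows that a converted subject who meets the definition is a success. The protocol does not say so in words.

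**3. Size**

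Inputs: n = 12 (Section 10.4); guide of 40% or higher (Synopsis and Section 3); exact binomial 95% interval (Section 10.2.1). For x successes, the lower limit is the 2.5% quantile of Beta(x, n − x + 1) and the upper limit is the 97.5% quantile of Beta(x + 1, n − x).

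The plan's own example, 6/12, gives 0.211 to 0.789, matching the stated 0.21 to 0.79.

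Each reclassified subject moves the rate by 1/12 = 8.3 points. The guide needs 0.40 × 12 = 4.8, so at least 5 successes. The number of converted successes is not given; 0 to 3 is assumed:

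| Observed successes | 0 converted | 1 | 2 | 3 |
|---|---|---|---|---|
| 5 | 41.7% | 33.3% | 25.0% | 16.7% |
| 6 | 50.0% | 41.7% | 33.3% | 25.0% |
| 7 | 58.3% | 50.0% | 41.7% | 33.3% |

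Exact 95% intervals: 5/12, 15.2% to 72.3%; 4/12, 9.9% to 65.1%; 3/12, 5.5% to 57.2%.

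The chance of at least 5 CNI-free successes, as Binomial(12, p(1 − s)) with p the true insulin-independence rate and s the share of successes on a CNI (both assumed):

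| p | s = 0 | s = 0.1 | s = 0.2 | s = 0.3 |
|---|---|---|---|---|
| 0.5 | 0.806 | 0.696 | 0.562 | 0.417 |
| 0.4 | 0.562 | 0.446 | 0.331 | 0.225 |

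**The case against.** Much of the spread between sections is discretion. Most of the rules say may, their triggers differ (troughs in Sections 3 and 5.2.1.6, tolerability in 5.2.1.3 and 5.2.1.4), and Section 5.7.1 lets the site investigator choose an alternative regimen. Sections 3 and 5.2.1.4 can be read together, because 5.2.1.6 supplies the MMF on which 5.2.1.4 is silent. That stands, so not every difference is a contradiction. It does not resolve the four mismatches set out in the working. Table 2 applies only to subjects on a CNI, which limits its reach, but it still offers those subjects responses that fit no stated CIT-05 regimen.

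Intention to treat is applied consistently and is a sound estimate of a policy of starting CNI-free with a fallback. That also stands, and is why it should remain primary. Leaving details to the analysis plan does not remove the problem, since the mismatch is between the outcome rule and the objectives that the protocol itself states.

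A reader might infer that converted successes were sustained by tacrolimus, so that the result is biased toward the experimental regimen. The documents do not establish this. Section 1.1 calls tacrolimus toxic to β cells and says CNIs halve β-cell secretory capacity, so conversion could also lower insulin independence. Only the classification effect has a fixed direction: including successes on a CNI cannot lower the apparent CNI-free rate.

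The information is partly collected. Regimen change is tabulated as a safety endpoint, tacrolimus levels are scheduled for converted subjects, and Section 10.3.3 permits summaries of medication by one-year outcome. That summary is optional and does not address Day 75.

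**Conclusion.** The concern holds in two parts. The rules conflict on whether MMF can replace sirolimus or only be added, on the trough that triggers a change, on the response to CNI nephrotoxicity, and on whether tacrolimus is a maintenance drug of this protocol. And the outcome rule counts successes on a CNI while Sections 2.1 and 2.2 read the rate as that of a regimen without tacrolimus.

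The size is 8.3 points per converted success, enough for one subject to move 5/12 across the 40% guide. The conversion rate is unknown; if nobody converts, the estimate is unaffected. A reader might treat 40% as a pass mark that conversions could wrongly satisfy. The protocol says only that such a rate would count as high and that further study may then be considered, so it is a guide, and the wide intervals around 4/12 and 5/12 overlap almost entirely. Nor do the documents support replacing the primary estimate, or judging the 40% guide and the Section 2.2 question on a CNI-free composite alone. That would score a subject converted for a side effect as not achieved despite full graft function.

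**What to change.** Reconcile Sections 3, 5.2.1.3 to 5.2.1.7, 5.6 and 5.7.1.5 so that they give one consistent account of what may happen when sirolimus cannot be continued, and make Table 2 fit regimens that CIT-05 subjects can receive and agree with 5.2.1.4. The clinical team decides the content; no view is taken here on which rule is right.

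Keep the all-transplanted intention-to-treat estimate as primary. In Sections 10.2.1 and 10.2.2, add beside it the proportion insulin independent and free of any CNI since transplant, at Day 75 and Day 365, over all transplanted subjects, with an exact 95% interval and the number converted. State whether the CNI-free period runs from the first or the final transplant. Read the Section 2.1 and 2.2 conclusions and the 40% guide in the light of both figures.

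The cost is protocol wording and one tabulation from data already scheduled. The CNI-free rate can only be equal to or lower than the primary rate. It describes CIT-05 alone and should not be compared with CIT-07, where tacrolimus is standard.

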#### **Study Endpoints**

### 3.1 Primary Endpoint

The primary endpoint will be insulin-independence at  $75\pm 5$  days following the first islet transplant.

## **Insulin Independence Definition:**

Islet transplant recipients will be considered insulin-independent with full islet graft function if they are able to titrate off insulin therapy for at least 1 week and all of the following criteria are met:

- HbA1c  $\leq$ 7.0% or a  $\geq$ 2.5% decrease from baseline.
- fasting capillary glucose level should not exceed 140 mg/dL (7.8 mmol/L) more than three times in the past week (based on measuring capillary glucose levels a minimum of 7 times in a seven day period);
- 2-hour post-prandial capillary glucose should not exceed 180 mg/dL (10.0 mmol/L) more than three times in the past week (based on measuring capillary glucose levels a minimum of 21 times in a seven day period);
- fasting serum glucose level ≤126 mg/dL (7.0 mmol/L); if the fasting serum glucose level is >126 mg/dL (7.0 mmol/L), it must be confirmed in an additional one out of two measurements;
- evidence of endogenous insulin production defined as fasting or stimulated c-peptide levels  $\geq$  0.5 ng/mL (0.16 nmol/L).

#### 3.1.1 Secondary Endpoints

#### **Efficacy Endpoints**

At  $75 \pm 5$  days following the first and final transplant(s):

- The proportion of insulin-independent subjects
- The percent reduction in insulin requirements
- HbA1c
- MAGE
- LI
- Ryan hypoglycemia severity (HYPO) score
- Basal (fasting) and 90-min glucose and c-peptide derived from the mixed-meal tolerance test (MMTT)
- β-score
- C-peptide: (glucose X creatinine) ratio
- Acute insulin response to glucose (AIRglu), insulin sensitivity, and disposition index derived from the insulin-modified frequently-sampled IV glucose tolerance (FSIGT) test
- Glucose variability6 and hypoglycemia duration derived from the CGMS

• Quality of life (QOL) measures

If a third transplant occurs less than 75 days after the second transplant, the 75 day endpoint data for the second transplant will not be collected.

At  $365 \pm 14$  days following the first transplant

- The proportion of subjects with an HbA1c <7.0% at Day 365 AND free of severe hypoglycemic events from Day 28 to Day 365 inclusive
- The proportion of subjects receiving a second islet transplant
- The proportion of subjects receiving a third islet transplant

A severe hypoglycemic event is defined as an event with one of the following symptoms: memory loss; confusion; uncontrollable behavior; irrational behavior; unusual difficulty in awakening; suspected seizure; seizure; loss of consciousness; or visual symptoms, in which the subject was unable to treat him/herself and which was associated with either a blood glucose level <54 mg/dL [3.0 mmol/L] or prompt recovery after oral carbohydrate, IV glucose, or glucagon administration.

At  $365 \pm 14$  days following the first and final islet transplant:

- The proportion of insulin-independent subjects
- The percent reduction in insulin requirements
- HbA1c
- MAGE
- LI
- Clarke score
- HYPO score
- Basal (fasting) and 90-min glucose and c-peptide (MMTT)
- β-score
- C-peptide: (glucose X creatinine) ratio
- AIRglu insulin sensitivity, and disposition index derived from the FSIGT test
- CGMS
- OOL
- The proportion of subjects receiving a second islet transplant
- The proportion of subjects receiving a third islet transplant
- The rate of subjects with an HbA1c  $\leq$ 7.0% and free of severe hypoglycemic events)

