## 3.1.2 Additional Hypothesis Generating Endpoints:

At  $75\pm 5$  days following the second and third transplants, the following will be reported for the subset who receive a second transplant who also have data collected and also for the subset who receive a third transplant.

- the proportion of insulin-independent subjects
- the percent reduction in insulin requirements
- HbA1c
- MAGE
- LI
- HYPO score
- Basal (fasting) and 90-min glucose and c-peptide (MMTT)
- β-score
- C-peptide: (glucose X creatinine) ratio
- Acute insulin response to glucose (AIRglu), insulin sensitivity, and disposition index derived from the insulin-modified frequently-sampled intravenous glucose tolerance (FSIGT) test
- Glucose variability and hypoglycemia duration derived from the continuous glucose monitoring system® (CGMS)
- QOL

At  $365 \pm 14$  days following the last islet transplant will include the change in the following measures from the results obtained at  $75 \pm 5$  days following the last islet infusion:

- the proportion of insulin-independent subjects
- the percent reduction in insulin requirements
- HbA1c
- MAGE
- LI
- Clarke score
- HYPO score
- Basal (fasting) and 90-min glucose and c-peptide (MMTT)
- β-score
- C-peptide: (glucose X creatinine) ratio
- Glucose variability and hypoglycemia duration derived from the continuous glucose monitoring system® (CGMS)
- QOL

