# 5.2.2.1.1 Daclizumab (Zenapax®)

Daclizumab (Zenapax®) is a humanized anti-CD25 monoclonal antibody in clinical use since 1997 for prophylaxis against acute organ rejection in subjects receiving a kidney allograft. Please refer to applicable product labeling and the Package Insert for its known and potential risks to human subjects.

Five I.V. doses of daclizumab will be given with all subsequent islet transplants. The first dose will be 2 mg/kg and will be given within two hours prior to islet transplant. Doses 2 to 5 will be 1 mg/kg will be given every 2 weeks starting on day 14 after the subsequent transplant.

If a third transplant is deemed necessary and performed between 30 and 70 days after the second transplant, no additional doses of daclizumab will be given.

If a third islet transplant is deemed necessary and performed more than 70 days after the second transplant (see Section 7.5 for indications for subsequent transplants), all five doses of daclizumab will be repeated.

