The option of a **third islet transplant** under this protocol will be considered only if all of the following conditions are met:

- 1. The subject received greater than 4,000 IE/kg with the second transplant, but remains dependent on insulin for longer than one month after the second transplant.
- 2. There is evidence of partial graft function.
- 3. The CIT PIs, Site PIs, and the Steering Committee have determined that there were no relevant protocol deviations at the site.
- 4. The subject has been compliant with study monitoring and prescribed immunosuppressive therapy.
- 5. No evidence of a serious and life-threatening infection, AE, or other condition that precludes attempting an intraportal injection or continuation of the post-transplant treatment regimen.
- 6. No evidence of PTLD.
- 7. No evidence of progressive renal dysfunction, with blood creatinine rising above 2.0 mg/dL (177  $\mu$ mol/L).
- 8. No evidence of hypersensitization, allergic responses, or other potentially serious drug reactions to medications required by the protocol.
- 9. No evidence of abnormal liver ultrasound and LFTs within 1.5 times the ULN range.
- 10. PRA <50 by flow cytometry (assessment performed locally) and the alloantibody specificity not cross-reactive with antigen(s) present in the subsequent islet preparation in order to avoid unacceptable antigen(s).

Subjects who have completed 8 months of follow-up post-first transplant will no longer be eligible for additional islet transplants funded under this protocol. Subjects that do not meet the criteria for a subsequent transplant and do not have a functioning graft will enter a reduced follow-up schedule (Appendix 2).

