# 10.2.2 Secondary Endpoint

As a secondary analysis the proportion of subjects with insulin independence at 75 days after transplant will be compared to the proportion of subjects with insulin independence at the University of Pennsylvania in the CIT-07 study using an exact test for two proportions. The same proportion will also be compared to pooled analysis of all subjects in the CIT-07 study from the four CIT centers (see the Statistical Analysis Plan, SAP).

Dichotomous variables such as HbA1c classified as normal ( $\leq$ 7.0%) and non-normal ( $\geq$ 7.0%) will be analyzed in a manner similar to the primary analysis. Continuous variables such as HbA1c, AIRg and c-peptide response will be examined for normality of the distribution and if there is no compelling evidence that the distribution is non-normal, will be analyzed by computing the mean and calculating a 95% confidence interval using the student's t-distribution

If there is compelling evidence that the normal distribution does not apply a logarithmic, square root or other transformation will be done before analyzing the data. An estimate and a 95% confidence interval for each response will be calculated. In addition, the responses will be

compared to the responses in subjects at the University of Pennsylvania in CIT-07 (using an exact test for two proportions, or a t-test, possibly after transformation, for continuous variables).

The additional hypothesis generating endpoints of 3.1.2 and the additional endpoints in 3.1.3 will be analyzed similarly and all the data will be subject to exploratory analysis. For variables that are collected at regular follow up visits, regression models for longitudinal data will be used to examine the responses over time for both dichotomous and continuous variables.

Values will not be imputed for missing secondary endpoints. The frequency of missing data will be reported.

There are a very large number of secondary endpoints. By examining multiple secondary endpoints it is likely that some variables will be found significantly different between the subjects in this study and those from the University of Pennsylvania in CIT-07, but these findings may be Type I errors. Appropriate qualifiers will be reported with any findings which are nominally significant at the 0.05 level or less and such results should be interpreted with extreme caution.

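### The hypothesis-generating Day 75 insulin-independence rate after the second transplant leaves out subjects given an early third transplant, an exclusion that depends on the outcome and can only raise the rate

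*Protocol*

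**What the plan says.** All references are to the protocol; the SAP was not available.

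- **Collection (Section 3.1.1, efficacy endpoints).** When any "third transplant occurs less than 75 days after the second transplant, the 75 day endpoint data for the second transplant will not be collected".
- **Reporting (Section 3.1.2).** Day 75 results after the second transplant are given "for the subset who receive a second transplant who also have data collected". The first item in the list is "the proportion of insulin-independent subjects".
- **Who can have a third transplant (Section 7.5.1).** Every listed condition must hold. One is that the subject "remains dependent on insulin for longer than one month after the second transplant". Another is evidence of partial graft function, a state that the same section reserves for recipients who do not meet the insulin-independence criteria.
- **Early third transplants are provided for (Section 5.2.2.1.1).** The daclizumab rules include a clause that begins "If a third transplant is deemed necessary and performed between 30 and 70 days after the second transplant". Section 5.2.2.1.2 has the same clause for basiliximab.
- **Missing data (Section 10.2.2).** "The additional hypothesis generating endpoints of 3.1.2 and the additional endpoints in 3.1.3 will be analyzed similarly" to the secondary endpoints, for which the rule is: "Values will not be imputed for missing secondary endpoints". The frequency of missing data is to be reported.
- **Contrast (Section 10.2.1).** For the primary endpoint, an unevaluated subject counts as a failure unless a later evaluation exists that precedes any further transplant.
- **Conflict (Section 7.6, also 7.7).** Insulin independence is to be assessed at 75 ± 5 days after each transplant, with no exception for an early third one.

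**The concern.** Read together, these rules make membership of the analysis set depend on the result being measured. A subject doing well after the second transplant cannot receive a third and so cannot be removed. A subject doing badly can receive one, and if that happens before Day 75 the subject leaves both the data and the denominator. The number reported is then the rate of independence among recipients who had no early third transplant. A reader would take it as the rate after a second transplant.

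What is at stake is one descriptive estimate in a study of 12 subjects. In groups this small, one or two removed subjects can change it visibly, and always in the favourable direction.

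**Working it through.** **Inputs.** The documents state no figure for this estimate, and they give no expected number of second transplants, successes or early third transplants. Let

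- m = subjects receiving a second transplant (at most 12, Section 10.4),
- s = those insulin independent at Day 75 after it,
- k = those given a third transplant before Day 75 after the second.

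**Step 1: can a removed subject be a success?** Section 7.5.1 requires continued insulin dependence beyond one month and partial graft function. So none of the k subjects was insulin independent when re-transplanted. Once the third graft is in place, success of the second alone can no longer be observed. All s successes therefore lie among the m − k who remain.

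**Step 2: what is reported.** Under Sections 3.1.1, 3.1.2 and 10.2.2 the rate is s/(m − k). With all recipients in the denominator it is s/m. The ratio is

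[s/(m − k)] ÷ [s/m] = m/(m − k) ≥ 1,

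with a strict increase whenever k > 0 and s > 0. The rate never falls. With k = 1 the relative increase is 1/(m − 1), for example 25% at m = 5 and 11% at m = 10.

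**Step 3: check of the interval method.** The exact (Clopper-Pearson) interval for 6 of 12 is 0.2109 to 0.7891, which agrees with the 0.21 to 0.79 printed in Section 10.4.

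**Step 4: illustrations.** All m, s and k below are assumed; 95% exact intervals are in brackets.

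| m | s | k | As written, s/(m − k) | All recipients, s/m | Shift |
|---|---|---|---|---|---|
| 5 | 2 | 1 | 2/4 = 50% (7–93%) | 2/5 = 40% (5–85%) | +10 points |
| 5 | 2 | 2 | 2/3 = 67% (9–99%) | 2/5 = 40% (5–85%) | +27 points |
| 6 | 3 | 1 | 3/5 = 60% (15–95%) | 3/6 = 50% (12–88%) | +10 points |
| 6 | 3 | 2 | 3/4 = 75% (19–99%) | 3/6 = 50% (12–88%) | +25 points |
| 8 | 4 | 2 | 4/6 = 67% (22–96%) | 4/8 = 50% (16–84%) | +17 points |
| 10 | 5 | 1 | 5/9 = 56% (21–86%) | 5/10 = 50% (19–81%) | +6 points |

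Across m = 4, 6, 8 and 10 with k = 1 to 3 and half of m independent, where that is possible, the shift runs from 6 to 50 points.

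**Step 5: which endpoints are touched.** The Section 3.1.1 efficacy endpoints are defined after the first and the final transplant. A subject with an early third transplant still contributes to both, because the third is then the final one. The primary endpoint concerns the first transplant only. The distortion is confined to the second-transplant results in Section 3.1.2.

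**The case against.** Several points on the other side stand.

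- **The tier is low.** The collection rule sits in the secondary-endpoint section, so a reader might infer that a secondary endpoint is biased. It is not: the affected estimate is labelled hypothesis generating. The 40% benchmark for further study refers to the first transplant.
- **Much is disclosed.** Section 3.1.2 names its subset, Section 10.2.2 reports how much is missing and urges extreme caution with nominally significant findings, and the proportions receiving second and third transplants are reported. A careful reader could suspect the selection. Disclosure does not correct the rate, however.
- **Certain failure at Day 75 is more than the documents show.** A reader might infer that every removed subject would have failed at Day 75. Section 7.5.1 establishes dependence beyond one month, not status at Day 75 without the third transplant. A late responder is possible. Counting these subjects as failures is an analytic choice, though it is the one Section 10.2.1 already makes for the primary endpoint.
- **Frequency is unknown.** A reader might infer from the 30-to-70-day clauses that early third transplants are expected. The clauses are conditional, Section 7.5.1 sets ten conditions, and Section 3 aims at no more than two procedures.
- **Bias against CIT-07 cannot be judged.** A reader might infer that the comparison is tilted. That depends on CIT-07's collection rule and its frequency of early third transplants, and the protocol gives neither.

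The intervals in the illustrations also overlap almost completely. That reflects small numbers; it does not remove a shift whose direction is fixed by rule.

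**Conclusion.** The point holds for one estimate: the proportion insulin independent at Day 75 after the second transplant in Section 3.1.2. The exclusion is outcome-dependent by construction, and the reported rate is at least s/m and higher whenever k > 0 and s > 0. That conclusion needs only the protocol's own rules. The size is not known; every figure in the table rests on assumed m, s and k. The other Day 75 measures after the second transplant are reported on the same selected subset.

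The primary endpoint and the secondary endpoints after the first and final transplants are intact, and nothing can be concluded about the CIT-07 comparison. This is a defect worth correcting in a descriptive result; it does not threaten the trial's main conclusion.

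**What to change.** 1. In Sections 3.1.2 and 10.2.2, for the binary endpoint, state that all second-transplant recipients stay in the denominator. A subject given a third transplant before Day 75 after the second is counted as not insulin independent after the second. Report the number so classified.
2. For continuous measures, do not carry values forward. Appendix 1 restarts at each transplant and first schedules HbA1c, MMTT, FSIGT, CGMS, MAGE, LI, HYPO and β-score at Day 75. The last scheduled value before an early third transplant would therefore usually describe the first graft. Report these measures as conditional on no third transplant before Day 75, with the number excluded.
3. Reconcile Sections 3.1.1 and 3.1.2 with Sections 7.6 and 7.7 on whether the Day 75 assessment follows every transplant.

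The binary change needs no new visit or data, because the transplant date and insulin dependence are already recorded. The cost is a few sentences in the protocol, mirrored in the SAP. The reported second-transplant rate becomes somewhat less favourable, and a possible late responder is counted as a failure.
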